#### 4.4 General Guidelines

Following registration, patients should begin protocol treatment as soon as possible. Issues that would cause treatment delays should be discussed with the Principal Investigator. If a patient does not receive protocol therapy following registration, the patient's registration on the study

may be canceled. The Clinical Research Site (CRS) must notify the CITN Coordinating Center of cancellations as soon as possible.

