Local reading (investigator assessment with site radiology reading) will be used to determine subject eligibility and for subject management. Radiologic scans may be sent to a central vendor for evaluation.

11.1.1.7 *Duration of Response*

Duration of overall response: The duration of overall response is measured from the time measurement criteria are met for CR or PR (whichever is first recorded) until the first date that recurrent or PD is objectively documented (taking as reference for PD the smallest measurements recorded since the treatment started).

The duration of overall CR is measured from the time measurement criteria are first met for CR until the first date that PD is objectively documented.

Duration of stable disease: SD is measured from the start of the treatment until the criteria for progression are met, taking as reference the smallest measurements recorded since the treatment started, including the baseline measurements.

ORR12: Patients who have a response duration of at least 12 months.

11.1.1.8 *Progression-Free Survival*

PFS is defined as the duration of time from start of treatment to time of progression or death, whichever occurs first.

11.1.1.9 *Response Review*

No review of response rate is contemplated. Investigator determined responses will be chronicled.

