##### *Progression-free survival (PFS)*

is defined as the time from enrollment to PD or death, whichever occurs earlier, based upon investigator assessment. Patients without documented PD/death will be censored at the last disease assessment date.

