**Summary Analysis Strategy for Efficacy Endpoints**

Endpoint/Variable (Description, Time Point)	Statistical Method	Analysis Population	Missing Data Approach
Primary:			
Overall response rate (ORR) per global assessment of Mycosis Fungoides and Sézary Syndrome (confirmed & investigator assessed)	Binomial proportion	Evaluable population as defined	Subjects without any efficacy evaluation will be excluded; if one compartment is missing data, that compartment will be considered non-response
Secondary:			
Time to Response (TTR)	Simple statistics	All responders	Non-responders are excluded in analysis
Duration of Response (DOR)	Kaplan-Meier method	All responders	Non-responders are excluded in analysis; censored at last f/u or start of new significant therapy
Progression-free survival	Kaplan-Meier method	All efficacy or safety evaluable patients	Censored at last f/u or start of new significant therapy

Endpoint/Variable (Description, Time Point)	Statistical Method	Analysis Population	Missing Data Approach
Event-free survival	Kaplan-Meier method	All efficacy or safety evaluable patients	Event is defined by early termination due to toxicity, start of new significant therapy, PD, or death of any cause
Rate of overall response duration beyond 12 months (ORR12) per global assessment of Mycosis Fungoides and Sézary Syndrome (confirmed & investigator assessed)	Binomial distribution	Evaluable DOR beyond 12 months for evaluable population.	Subjects without any efficacy evaluation will be excluded; The ORR12 is the proportion of ORR times conditional probability of DOR beyond 12 months. If one compartment is missing data, that compartment will be considered non-response. Censored at last f/u. Start of new significant therapy before 12 months will be considered as failures.

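### Group 1 PFS carries two conflicting censoring rules, and no definition of duration of response counts death

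*Combined protocol and SAP*

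**What the plan says.** **PFS in the text.** Section 13.1.1.2 says that PFS "is defined as the time from enrollment to PD or death, whichever occurs earlier, based upon investigator assessment". It adds: "Patients without documented PD/death will be censored at the last disease assessment date". Section 1.2.1.4 gives the same rule. Neither mentions new therapy.

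**PFS in the table.** In the PFS row of the Summary Analysis Strategy for Efficacy Endpoints (end of section 13.1.1.3), patients are "censored at last f/u or start of new significant therapy". It does not mention the last disease assessment.

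**PFS origin.** Section 11.1.1.8 starts the clock elsewhere: "PFS is defined as the duration of time from start of treatment to time of progression or death, whichever occurs first".

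**DOR.** Sections 1.2.1.3 and 13.1.1.2 run it from first response to progression. Section 11.1.1.7 ends it at documented recurrent or progressive disease. The table row reads "Non-responders are excluded in analysis; censored at last f/u or start of new significant therapy". None of the four names death, either as an event or as a reason for censoring.

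**Follow-up.** Section 5.5 plans disease assessment every 12 weeks for patients who stop without progression, until new treatment, progression, death or study end. It words this as a best-effort requirement and lets status be collected by telephone. After progression or new anticancer treatment, patients are followed for survival only.

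**The concern.** The text and the table are both current, and nothing says which takes precedence. Two analysts could follow the plan faithfully and report different PFS curves from the same data.

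The DOR problem is of another kind. The definition is consistent, but incomplete. A responder who dies without documented progression has no DOR event, so the only rule left to apply is the censoring one.

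This is a single-arm trial. Section 2.4.5 hopes to improve PFS, with favourable DOR, over pembrolizumab alone, for which section 2.4.3 reports a median PFS of 44 weeks. Any such comparison depends on the event and censoring conventions. Section 13.1.2 also uses DOR and PFS in the biomarker log-rank tests. A convention left open until the data are seen can be chosen for its result.

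**Working it through.** The plan gives no target figure for PFS or DOR, so there is none to reproduce. The check compares the rules and then sizes the differences under stated assumptions.

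**1. Where the PFS rules differ**

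| Patient without progression | Text (1.2.1.4, 13.1.1.2) | Table |
|---|---|---|
| Alive, assessed every 12 weeks, no new therapy | Censored at last assessment | Censored at last follow-up, nearly the same date |
| Assessments lapse, telephone contact continues | Censored at last assessment | Censored later, at last contact |
| Starts new therapy, later dies | Event at death | Censored at new therapy |

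The third row is the main conflict. Section 5.5 makes it observable, because survival follow-up continues after new therapy.

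**2. Size of the third row.** Assumptions: exponential PFS with median 44 weeks (section 2.4.3); progression seen on a 12-week grid; independent exponential start of new therapy; exponential survival afterwards, observed for up to 52 weeks. The last grid visit before week 52 is week 48, so the base estimate is 2^(−48/44) = 46.9%. Simulated 52-week Kaplan-Meier estimates (600,000 patients):

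| New therapy without progression by week 52 | Text rule, median later survival 104 / 52 / 26 weeks | Table rule |
|---|---|---|
| 5% | 46.7 / 46.5 / 46.1% | 46.9–47.0% |
| 10% | 46.4 / 45.9 / 45.2% | 46.9–47.0% |
| 20% | 45.7 / 44.8 / 43.3% | 46.9–47.0% |
| 30% | 45.0 / 43.5 / 41.2% | 46.9–47.0% |

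The gap runs from 47.0 − 46.7 = 0.3 to 47.0 − 41.2 = 5.8 points. With 30 patients the standard error is √(0.47 × 0.53 / 30) = 0.091, about 9 points.

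**3. Size of the second row.** It is zero if the 12-weekly assessments in section 5.5 are kept. If 10 to 30% drop out of assessment and contact continues for 12 to 52 weeks, the table rule raises the 52-week estimate by about 1 to 9 points. That requires departing from section 5.5.

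**4. DOR without death.** Suppose a share q of a constant hazard of response ending is death without progression and before new therapy. Censoring those deaths leaves hazard (1 − q)h, so the median is multiplied by 1/(1 − q):

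- q = 5%: 1.05
- q = 10%: 1.11
- q = 20%: 1.25
- q = 30%: 1.43

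A small example: 17 responders, with progression at months 4, 7 and 10.

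- One death, at month 3. Censored: 15/16 × 14/15 × 13/14 = 13/16 = 81.2% in response at 12 months. Counted: 13/17 = 76.5%.
- Deaths at months 3 and 6. Censored: 15/16 × 13/14 × 12/13 = 80.4%. Counted: 12/17 = 70.6%.
- Deaths at months 3, 6 and 9. Censored: 15/16 × 13/14 × 11/12 = 79.8%. Counted: 11/17 = 64.7%.

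**5. Origin.** Enrollment and start of treatment should be close, since section 4.4 says "Following registration, patients should begin protocol treatment as soon as possible". The discrepancy is probably a matter of days.

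**The case against.** **Materiality.** Every rate above is assumed, each PFS gap lies below the standard error, and no success threshold rests on PFS or DOR. This limits the weight of the point but does not remove it: sampling error is no reason to keep two rules that give two answers from one dataset.

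**Follow-up as planned.** If the section 5.5 assessments are kept, last follow-up and last assessment nearly coincide before new therapy. This stands, and it reduces the PFS conflict mainly to deaths after new therapy.

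**DOR as a choice.** Ending DOR at progression is applied consistently, and event-free survival already counts death and new therapy. A responder who starts new therapy before dying is censored earlier in any case. So this is a gap rather than a contradiction, and the bias is confined to deaths before new therapy. Event-free survival is a different endpoint and does not mend the DOR curve. Section 13.1.5.2 treats early deaths as failures only for the response rate.

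**Stronger readings that the documents do not support.**

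- *ORR12.* A reader might infer that the table contradicts itself, because the DOR row censors new therapy while the ORR12 row says "The ORR12 is the proportion of ORR times conditional probability of DOR beyond 12 months" and then "Censored at last f/u. Start of new significant therapy before 12 months will be considered as failures". But sections 1.2.1.6, 11.1.1.7 and 13.1.1.2 describe ORR12 through patients whose response lasts at least 12 months, two of them as a percentage of all patients, and the row names a binomial method. With R responders among N patients and k lasting 12 months, (R/N) × (k/R) = k/N. The row's own failure rule then applies and there is no discrepancy. Only the mention of censoring is out of place.
- *Palliative radiation.* Its absence from the PFS definitions might look like a conflict, but section 5.3.1.2 states how it counts for PFS.
- *Group 2.* Its PFS row in section 13.2.1 also censors at last follow-up or new therapy, but no Group 2 text states a different censoring rule.

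**Conclusion.** The point holds for Group 1 PFS and DOR. PFS has two incompatible censoring rules, worth 0.3 to 5.8 points at 52 weeks under the assumed rates of new therapy and later death, plus a minor mismatch of origin. DOR omits death. Followed as written, the plan inflates median DOR by 5 to 43% if 5 to 30% of response endings are deaths without progression and before new therapy, under a constant hazard. The documents give none of these rates, so the sizes are illustrations; the conflict and the direction of the DOR bias do not depend on them. A reader should not carry this over to the main result: primary ORR, type I error, power and sample size are unaffected.

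**What to change.** 1. Use one Group 1 PFS definition with one stated origin in sections 1.2.1.4, 11.1.1.8 and 13.1.1.2 and in the efficacy table.
2. In the PFS and DOR rows of that table, replace last follow-up with the last disease assessment.
3. State the same new-therapy rule in text and table, including how a death after new therapy is counted.
4. Count death from any cause as a DOR event in sections 1.2.1.3, 11.1.1.7 and 13.1.1.2 and in the table.
5. Clarify ORR12 without changing it: delete the mention of censoring at last follow-up. State that it is the number of responders with at least 12 months of documented response divided by all evaluable patients, with new therapy, death or loss before 12 months counted as not achieving it.

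The cost is protocol and SAP wording, using dates already collected. Durability estimates may come out slightly less favourable.

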##### *Time to response (TTR)*

##### *Duration of response (DOR)*

is defined as the time interval between the date of first response (CR/PR) and the date of progression.

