##### *ORR12*

Percentage of all patients who have a response duration of at least 12 months (ORR12)

**Hypothesis:** Combination immunotherapy of MK-3475 (pembrolizumab) and IFN-gamma (Actimmune®) will have acceptable safety/tolerability profile in previously treated Mycosis Fungoides/Sézary Syndrome population and meaningful clinical activity will be reflected in other clinical outcome parameters including DOR, PFS, EFS and ORR12.

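### ORR12 (Group 1) is defined as ORR times a censored 12-month duration probability but assigned a binomial method; the two agree only if no responder is censored before 12 months

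*Combined protocol and SAP*

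**What the plan says.** ORR12 is a Group 1 secondary endpoint. Sections 1.2.1.6 and 13.1.1.2 define it as the percentage of all patients whose response lasts at least 12 months. The efficacy analysis table in Section 13.1.1.3 then gives:

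- **Method:** "Binomial distribution".
- **Population:** "Evaluable DOR beyond 12 months for evaluable population".
- **Estimator:** "The ORR12 is the proportion of ORR times conditional probability of DOR beyond 12 months".
- **Censoring and new therapy:** "Censored at last f/u. Start of new significant therapy before 12 months will be considered as failures".

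The DOR row of the same table uses Kaplan-Meier in responders, with the rule "Non-responders are excluded in analysis; censored at last f/u or start of new significant therapy". Section 13.1.1.2 says that DOR "is defined as the time interval between the date of first response (CR/PR) and the date of progression", so death is not named as an event.

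The plan does not say how a responder censored before 12 months enters the ORR12 calculation, how the interval for the product is formed, or which duration curve supplies the second factor. Section 13.1.5.2 asks for 95% confidence intervals without naming a type.

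**The concern.** The row joins three instructions: a product estimator, censoring at last follow-up and a binomial method. Once a responder is censored before 12 months, an analyst must choose. One choice is to compute the product and put a binomial interval around it, which ignores the information lost to censoring. The other is to force a yes/no count by failing or dropping the censored responder, which shifts the estimate.

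The situation is foreseeable. Recruitment is continuous, the Schema estimates a 3-year trial, and no data cut-off is given for ORR12. Disease monitoring after stopping without progression is on a best-effort basis and ends at new treatment or end of study (Section 5.5).

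The second risk is practical. The only duration curve specified is the DOR row's, which censors new therapy, whereas ORR12 counts it as failure. A programmer could reuse that curve without noticing. At stake is the reported durable-response rate in an open-label, single-arm trial, where the analyst should not be free to choose among readings after seeing the data.

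**Working it through.** The plan gives no target, power or interval width for ORR12, so there is no figure to reproduce. The sample size of 30 and the 17-responder success threshold come from Sections 13.1.1.4 and 13.1.3.1. The 12-month duration probability and the censoring and new-therapy rates below are assumptions.

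**1. When the methods agree.** Let p be ORR, S the 12-month probability among responders, n the patients. With no early censoring and new therapy a failure, the product is the count of long responders over n. Its variance is

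S²p(1−p)/n + p²·S(1−S)/(np) = pS(1−pS)/n,

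which is the binomial variance. Example: 17 of 30 respond and 11 pass 12 months. Then 17/30 × 11/17 = 11/30 = 36.7%, with SE 0.088 by both formulas.

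**2. Worked example with censoring (assumed data).** Of 17 responders, 4 progress (months 3, 5, 7, 9), 2 start new therapy without progression (6, 8), 3 are censored (4, 6.5, 10) and 8 pass 12 months.

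- New therapy as failure (the row's rule): S = 16/17 × 14/15 × 13/14 × 11/12 × 10/11 × 9/10 = 0.612. ORR12 = 17/30 × 0.612 = 34.7% (logit-scale 95% interval 19.6 to 53.6). SE by Greenwood and delta method 0.090; naive binomial √(0.347 × 0.653/30) = 0.087.
- DOR row's curve (new therapy censored): S = 16/17 × 14/15 × 11/12 × 9/10 = 0.725. ORR12 = 41.1%.
- Count, censored as failures: 8/30 = 26.7%.
- Count, censored dropped: 8/27 = 29.6%.

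**3. Average behaviour under early censoring.** Assume n = 30, p = 0.60, S = 0.60, exponential durations, and a share c of responders given a uniform censoring time within 12 months. True ORR12 is 0.60 × 0.60 = 36%.

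- Censored as failures, c = 20%: 0.36 × 0.80 = 28.8% (simulated 28.7%).
- Censored dropped, c = 20%: the share of responders actually censored is 0.20 × 0.40/0.511 = 0.157, where 0.511 = −ln 0.60. So 0.288/(1 − 0.60 × 0.157) = 31.8% (simulated 31.7%).
- Product with a binomial SE, 6,000 simulated trials:

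| c | SD of product | mean binomial SE | shortfall |
|---|---|---|---|
| 0% | 0.088 | 0.086 | about 2% |
| 20% | 0.092 | 0.086 | about 6% |
| 35% | 0.095 | 0.086 | 10 to 11% |
| 50% | 0.100 | 0.085 | 15 to 16% |

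The shortfall ranges span repeat runs. A second scenario (ORR 57%, S 60%, true 34.2%) gives the same pattern: counting censored as failures averages 31.0/27.4/24.0% at 10/20/30% censoring, while the Kaplan-Meier product stays at 34.1 to 34.5%.

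**4. Reusing the DOR curve.** If a fraction f of response endings are new therapy, the reused curve gives 0.60 × 0.60^(1−f): 37.9%, 39.9% and 42.0% at f = 10/20/30%, against 36%, or +1.9, +3.9 and +6.0 points. If instead 10% or 20% of responders start new therapy without progression before 12 months (ORR 57%, S 60%), the true values are 0.342 × 0.90 = 30.8% and 0.342 × 0.80 = 27.4%, against about 34%: roughly +3.5 and +7 points.

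**The case against.** A reader might infer that the ORR12 and DOR rows contradict each other on new therapy. The text does not support that. The ORR12 row states its own rule and never says that the DOR row's curve is the second factor. Endpoints may differ: in the same table PFS censors at new therapy while EFS counts it as an event. Followed literally, the ORR12 row already treats new therapy as failure. What remains is a warning against reusing the DOR curve.

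A reader might also infer that the estimate and interval are simply wrong. They are exact if no responder is censored early, and that may hold for most: treatment can run 2 years, and assessment continues every 12 weeks after stopping without progression. But without a stated cut-off, early censoring cannot be ruled out.

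Nor do the documents support saying that any binomial interval is too narrow. No interval type is specified. In the scenario of step 3, a Wald binomial interval around the product covers 92/90/89% at 20/35/50% censoring, but already only 93.7% with none. An exact-type binomial interval covers about 96/95/93 to 94%. A plain Wald-form delta interval gives 94/93/93%, so carrying both variances is not enough unless the scale is also right. The variance form is therefore the smaller issue; how censored responders are counted is the larger.

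**Conclusion.** The point holds as a mismatch between the named method and the defined estimator, not as a demonstrated error. With early censoring, the product keeps its target but a binomial standard error understates its spread, and either literal count is biased low by about 4 to 7 points at 20% censoring (36% against 32% or 29%). In the worked example the possible readings run from 26.7% to 41.1% on the same data, a spread of about 14 points; its upper end requires overriding the row's own new-therapy rule.

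These sizes rest on assumed duration, censoring and new-therapy rates and on censoring unrelated to outcome. ORR12 has no target, test or decision rule. Futility and success rest on ORR alone, so the primary conclusion does not change. It is still worth settling before analysis, because ORR12 is a named secondary endpoint and part of the stated hypothesis of meaningful clinical activity.

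**What to change.** In the ORR12 row:

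- Replace the binomial entry with ORR times the Kaplan-Meier 12-month probability among responders. Events are progression, death and start of new significant therapy; censoring is at last follow-up.
- State that this curve is derived for ORR12 and is not the DOR row's curve.
- Give a 95% interval by bootstrap, or by the delta method on the logit scale with both variance terms. The latter covers about 96% throughout the step 3 scenario. Avoid the plain Wald form.
- Use one denominator, all evaluable patients, in place of the evaluable-duration subset.
- Keep the plain proportion, with unresolved cases as failures and an exact interval, as a sensitivity analysis only, because it is biased low.

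The cost is a wording change and a few lines of code, with a slightly wider interval. No change to sample size, visits or the primary analysis is needed.

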#### 13.1.1.4 *Interim Safety and Futility Analyses*

- One interim safety analysis will be performed in this study when 12 patients are evaluable for toxicity at pre-C4 (week 10) of the study. If at that time, 4 or more patients have experienced study drug related serious adverse events (SAEs), we will conclude that the combination immunotherapy regimen is too toxic and accrual will stop.
- The properties of interim safety stopping rule are given in the table below.

True Probability of Study Drug Related SAEs (ptox)	Probability of Stopping Early (pstope)
0.10	0.026
0.14	0.075
0.18	0.155
0.22	0.261
0.26	0.382
0.30	0.507

One interim futility analysis will be performed in this study. Results will be reviewed by the participating institutions/investigators, CITN, NCI/CTEP, and participating industry sponsors (Horizon and Merck).

The statistical criterion for success requires ORR that is greater than 37% (null) and at least 65% (alternative). This is a single stage trial. Patients will be recruited continuously. We will perform the interim futility analysis when 12 patients have been followed for 6 months. If ORR is less than 33% (4 or less CR+PR), the trial will stop and we will accept the null that combination therapy is no better than monotherapy. The probability of

stopping at interim futility analysis under the null and alternative are 52% and 2% respectively.

Otherwise, the trial will continue until we reach 30 patients. If ORR is at least 57% (17 or more CR+PR) at the final analysis, we will accept the alternative that combination therapy is significantly better than monotherapy. The type I error rate is 2%. The power is 87%.

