We hypothesize that combining an anti-PD-1 agent, MK-3475 (pembrolizumab), with IFN-gamma, an immune-augmenting agent with a wide range of immune activity, would result in a synergistic or complementary immune activity and yield superior clinical outcome with improved ORR and PFS in similar cohort of Mycosis Fungoides/Sézary Syndrome patients studied with MK-3475 (pembrolizumab) monotherapy. We would deem the combination successful if the ORR is 58% or greater, our primary efficacy endpoint. We also hope to improve the PFS with favorable DOR, our secondary endpoints.

With combination immune strategies, we are always mindful of possible additive toxicities, thus safety/tolerability is an important endpoint especially in our CTCL population where the disease course is often chronic and a curative outcome is not anticipated other than with an allogeneic HSC transplantation. Immune checkpoint blockade has been known to induce immune-mediated adverse events, although, anti-PD-1 agents have demonstrated a better safety profile than PD-L1 or CTLA-4 blockade [[Weber 2015](#)]; [[Larkin 2015](#)]. Our monotherapy with MK-3475 (pembrolizumab) has demonstrated an acceptable toxicity profile; however, we have observed a subset of patients experiencing grade 3 skin reactions and one patient with possible MK-3475 (pembrolizumab) related grade 3 pneumonitis which was reported as a serious adverse event (SAE). Interferons have been associated with anticipated immune activating cytokine related adverse events. Patients who receive continuous dosing of interferons suffer from constant symptoms that can lead to decreased quality of life and early termination of treatment. Thus, we plan to use an interrupted dosing strategy of IFN-

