#### 13.1.3 Sample Size/Accrual Rate

##### 13.1.3.1 *Power and Sample Size*

The statistical criterion for success requires ORR that is greater than 37% (null) and at least 65% (alternative). By adding an interim futility analysis, the sample size is 30

patients. The probability of stopping at interim futility analysis under the null and alternative are 52% and 2%, respectively. The type I error rate is 2%. The power is 87%. The expected sample sizes under the null and alternative are 21 and 30, respectively.

This is a single stage trial. Patients will be recruited continuously. We will perform the interim futility analysis when 12 patients have been followed for 6 months. If ORR is less than 33% (4 or less CR+PR), the trial will stop and we will accept the null that combination therapy is no better than monotherapy. Otherwise, the trial will continue until we reach 30 patients. If ORR is at least 57% (17 or more CR+PR) at the final analysis, we will accept the alternative that combination therapy is significantly better than monotherapy.

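### Treatment Group 1: the futility percentage contradicts its own count at 4 of 12 responders, and section 2.4.5 gives a success level (58%) that differs from the rule of 17 of 30

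*Combined protocol and SAP*

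**What the plan says.** The Treatment Group 1 interim look is set by patient number and follow-up: "We will perform the interim futility analysis when 12 patients have been followed for 6 months". The stopping rule in section 13.1.1.4 reads "If ORR is less than 33% (4 or less CR+PR), the trial will stop and we will accept the null". Section 13.1.3.1 repeats it ("If ORR is less than 33% (4 or less CR+PR), the trial will stop"), and sections 1.1.1, 5.2.1 and 13.1.1.1 carry the same pairing of percentage and count.

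If the trial goes on to 30 patients, the final rule in those five sections is "If ORR is at least 57% (17 or more CR+PR) at the final analysis".

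For a null ORR of 37% and an alternative of 65%, section 13.1.1.4 gives the probabilities of "stopping at interim futility analysis under the null and alternative are 52% and 2% respectively", with a type I error of 2% and power of 87%. Section 13.1.3.1 adds: "The expected sample sizes under the null and alternative are 21 and 30, respectively".

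The rationale in section 2.4.5 has a different success level: "We would deem the combination successful if the ORR is 58% or greater, our primary efficacy endpoint".

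**The concern.** The futility sentence gives a percentage and a count as if they were the same threshold, and at the boundary they are not. With 0 to 3 responders both say stop, and with 5 or more both say continue. With exactly 4 of 12 they give opposite instructions. No section says which half takes precedence, and the mismatch appears in every statement of the rule.

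The 58% in section 2.4.5 is not a rounding of 17/30. At the planned 30 patients it is a different cut-off, one responder higher, and the sentence ties it to the primary endpoint.

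Both points concern the decision rules for the primary endpoint, and section 13.1.1.4 sends the interim results to investigators, CITN, NCI/CTEP and the industry sponsors. If either boundary value occurred, the parties would be choosing the reading with the data in front of them.

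**Working it through.** **Inputs.** Null ORR p0 = 0.37 and alternative p1 = 0.65; interim n1 = 12; total N = 30; futility count 4 or fewer; success count 17 or more (all in section 13.1.1.4). Success level 58% (section 2.4.5).

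**Step 1: percentages against counts.**
- 4/12 = 33.3%, not below 33%. The largest count strictly below 33% is 3/12 = 25.0%.
- A smaller evaluable denominator does not help: 4/11 = 36.4%, 4/10 = 40.0%.
- 17/30 = 56.67%, which is printed as 57%.
- 0.58 × 30 = 17.4, so 58% needs 18/30 = 60.0%. With 29 evaluable patients, 17/29 = 58.6% would pass.

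**Step 2: formulas (exact binomial, two looks).** Let X1 ~ Bin(12, p) and X2 ~ Bin(18, p), futility count a and success count r.
- P(stop) = Σ from x = 0 to a of C(12, x) p^x (1 − p)^(12 − x)
- P(success) = Σ from x = a + 1 to 12 of P(X1 = x) · P(X2 ≥ r − x)
- E[N] = 12 + 18 · (1 − P(stop))

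**Step 3: reproduce the plan, then try the other readings.**

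| Rule | P(stop), p0 / p1 | Type I error | Power | E[N], p0 / p1 |
|---|---|---|---|---|
| Plan as stated | 52% / 2% | 2% | 87% | 21 / 30 |
| a = 4, r = 17 (the counts) | 52.49% / 2.55% | 2.15% | 86.57% | 20.55 / 29.54 |
| a = 3, r = 17 (literally below 33%) | 29.47% / 0.56% | 2.21% | 87.27% | 24.70 / 29.90 |
| a = 4, r = 18 (58% reading) | 52.49% / 2.55% | 0.86% | 77.61% | 20.55 / 29.54 |
| a = 4, r = 16 (for comparison) | 52.49% / 2.55% | 4.72% | 92.20% | 20.55 / 29.54 |

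For the counts, E[N] under the null is 12 + 18 × (1 − 0.5249) = 20.55, which rounds to the stated 21. The counts reproduce every stated figure on rounding except the stopping probability under the alternative: 2.55% matches the printed 2% only by truncation. Stopping at 3 or fewer fits neither 52% nor 21. Success at 16 or 18 fits neither 2% nor 87%.

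**Step 4: how often the boundaries occur.**
- Exactly 4 of 12: 0.5249 − 0.2947 = 0.2302 under the null; 0.0255 − 0.0056 = 0.0199 under the alternative.
- A trial that continued from 4 of 12 would need 17 − 4 = 13 or more of the remaining 18. That has probability 0.0026 under the null and 0.3550 under the alternative.
- Cost under the null of the literal percentage: 24.70 − 20.55 = 4.15 more patients on average, that is, 18 more patients in about 23% of null trials.
- Passing the interim and ending on exactly 17: 0.8657 − 0.7761 = 0.0896 under the alternative; 0.0215 − 0.0086 = 0.0129 under the null.

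**The case against.** The strongest reply is that the documents already resolve the futility rule. The count sits beside the percentage in all five places, and the printed 52% and 21 fit only a count of 4 or fewer. Even the wrong reading hardly moves the error rates: type I error and power still round to 2% and 87%. The 58% is a single background sentence with no denominator, count or error rate, and nothing suggests it would be applied at the final analysis. It also ceases to conflict if one patient is excluded as having no efficacy evaluation, which the efficacy summary table in section 13.1.1.3 allows.

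Most of this stands as to weight. The intent can be recovered, the design calculation is sound, and the 0.86% and 77.6% figures show that 58% is not the intended rule; they do not describe a test that the plan would run. The printed 57% is ordinary rounding and would not merit comment alone.

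The objection does not make the text consistent. Recovering the intent means recomputing the stopping probability, and no section says that the count governs. At the planned 30 patients, 58% and 17 of 30 remain different cut-offs. The objection is also right that stating a count does not say what applies if fewer than 30 patients are evaluable. That is a separate question about the analysis population.

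**Conclusion.** Both mismatches are real and minor. The intended rules are to stop at 4 or fewer of 12 and to declare success at 17 or more of 30, because of the cut-offs tried only these reproduce the plan's operating characteristics. The futility wording says below where at most is meant, and section 2.4.5 is out of line with the rule by one responder.

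The practical effect is confined to two outcomes: exactly 4 of 12 (23.0% under the null, 2.0% under the alternative) and passing the interim with exactly 17 of 30 (1.3% and 9.0%). At the first, the main cost of misreading is 18 further patients on a regimen that would then reach 17 responders with probability 0.26% if the null is true. At the second, the statistics section would declare success and the rationale would not.

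These figures assume independent binomial responses, all 12 and all 30 patients in the denominators, and the plan's own rates of 37% and 65%.

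**What to change.** In sections 1.1.1, 5.2.1, 13.1.1.1, 13.1.1.4 and 13.1.3.1, state the rules as counts, with percentages only as a gloss: stop for futility if 4 or fewer of 12 patients respond (at most 33.3%); declare success if 17 or more of 30 respond (at least 56.7%). In section 2.4.5, replace the 58% level with 17 or more of 30.

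The cost is wording in six places. Sample size, analysis population, stated type I error and stated power do not change. The edit should be made before either boundary can be observed. How the rules apply if fewer than 12 or 30 patients are evaluable should be handled separately, with the definition of the analysis population.
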